15.3 AUDITING

Quality assurance (QA) procedures are designed to ensure complete, timely, and accurate submission of data, and that protocol requirements and complications and/or adverse events are immediately identified.

In addition to the monitoring visits outlined above, an investigational site may undergo a QA audit. Noxopharm or their authorized representatives or a regulatory agency such as the FDA may conduct the audit. If the FDA requests an audit of the study site, the Investigator is required to inform Noxopharm or the monitoring CRO immediately.

16 ADVERSE EVENT REPORTING

16.1 DEFINITIONS

16.1.1 ADVERSE EVENTS

An AE is any unanticipated or unintended medical occurrence or worsening of a sign or symptom (including an abnormal laboratory finding) or disease in a study participant, that occurs after the informed consent is obtained, which does not necessarily have a causal relationship with the study condition, procedures or study agent(s). An AE can therefore be any unfavorable and unintended sign (including an abnormal laboratory finding), symptom, or disease temporally associated with the use of an investigational study product/procedure(s), whether or not related to the investigational study product/procedure(s).

This includes any occurrence that is new in onset or aggravated in severity or frequency from the baseline condition (including the physical examination), or abnormal results of diagnostic procedures (including laboratory test abnormalities).

Events should also be considered AEs if they:

- result in discontinuation from the study,
- require treatment or any other therapeutic intervention,
- require further diagnostic evaluation (excluding a repetition of the same procedure to confirm the abnormality),
- are associated with clinical signs or symptoms judged by the Investigator to have a significant clinical impact

Clinically Significant Laboratory Changes: It is the Investigator's responsibility to review the results of all laboratory tests as they become available. For each abnormal result, the Investigator needs to ascertain whether the abnormality presents a clinically significant change from baseline. If the change is due to the expected course of the patient's underlying disease (e.g. elevated cholesterol in a study of dyslipidemia), it is not considered an adverse event unless the abnormality is more severe than expected. A laboratory test may be confirmed by repeat testing or other diagnostic tests before being considered an adverse event. If the laboratory abnormality is a significant change from baseline for the patient, then it should be considered an adverse event.

An Adverse Event is not:

- a surgical procedure
- a situation where an untoward event did not occur, (e.g. an elective hospitalization)
- the disease being studied, unless progression is more severe than anticipated
- lack of efficacy
- baseline conditions that have not worsened in severity or frequency
- the puncture from venipunctures

Pre-existing conditions or illnesses which are expected to exacerbate or worsen are not considered adverse events and will be accounted for in the patient's medical history.

All adverse events are to be followed up for 30 days post the last dose of study drug or until resolution (whichever is sooner).

Adverse events reported by the patient or observed by the Investigator will be listed individually on an adverse event form in the eCRF. The signs and symptoms, time of onset, criteria for assessing causality to study drug ([Table 5](#)) and outcome categories should be defined ([Table 6](#)). In order to classify AEs and diseases, preferred terms and system organ classes will be assigned by the Sponsor to the original terms entered on the eCRF using the Medical Dictionary for Regulatory Activities (MedDRA) (Section 13.2.1).

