The MTD of the combination of NOX66 and doxorubicin will be determined over the first 21-day interval (Cycle 1) following monotherapy with NOX66 and in combination of doxorubicin-in 1 of 3 consecutive dose cohorts. The MTD of the combination will either be considered one dose level of NOX66 lower than the dose which produces ≥ 2 DLTs in 3 or 6 patients, depending if a DLT occurred in the first 3 patients, or the highest dose level tested (1800 mg daily) if the aforementioned condition does not occur. A DLT will be defined as a protocol-specified adverse event of toxicity Grade 3-4 (National Cancer Institute Common Terminology Criteria for Adverse Events [NCI-CTCAE] V 5.0) which is considered possibly, probably, or definitely related to the combination of NOX66 and doxorubicin (Section 8.3).

Since this is a multicenter trial, the sites are to notify the Sponsor or designee when a patient has been declared eligible to participate. After 3 patients have completed a 21-day treatment cycle of the combination of NOX66 and doxorubicin and all the safety data are available, assessment of toxicities and decisions about dose escalation and cohort expansion (see below) will be made by the SRC, which will include at least one Sponsor representative participating Investigators, and may also include a cardiologist or other external consultants at the Sponsor's discretion. Recommendations from the SRC could include 1) repeat a dose level, 2) await further safety data if follow-up is pending for patient(s) as determined by the Investigator(s), 3) discontinue the study, 4) escalate the dose to next possible level or 5) take other actions.

Three new patients will be entered at the next dose level of NOX66, if there were no DLTs or only 1 of 6 patients had a DLT at the end of the first cycle.

If no DLT is observed at 1800 mg (Cohort 3), dose escalation will be stopped. The proposed highest dose level (1800 mg) will be declared the MTD, and additional patients will be enrolled, if necessary, to ensure that a total of 6 patients are evaluated at this dose level.

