14.3.4 ADVERSE EVENTS

An AE will be deemed treatment emergent (TEAE) if it starts or worsens in severity or toxicity after the beginning of treatment, whether with idronoxil or with idronoxil + doxorubicin.

Adverse events will be coded using the MedDRA Dictionary, Version 22.0 (or higher). Treatment emergent adverse events will be summarized by MedDRA Preferred Term and System Organ Classification for each dose group. Separate summaries will be provided for TEAEs with onset prior to the first dose of doxorubicin, with onset during the first cycle of idronoxil+ doxorubicin therapy, and for TEAEs with onset after the end of the first treatment cycle.

The toxicity of an AE will be assessed by the NCI-CTCAE, Version 5.0. Summaries of TEAEs will be provided by dose group and toxicity grade. Summaries of TEAEs will also be provided by dose group and Investigator-reported severity and by dose group and Investigator-reported relationship to study treatment.

A summary will be provided of the overall incidence and the incidence of component terms for the Standardized MedDRA Queries (SMQs) for Cardiac Failure and for Cardiomyopathy.

A separate summary will be provided of Serious Adverse Events (SAEs) by dose group. Summaries will be presented for all SAEs, for treatment-emergent SAEs, for treatment-emergent SAEs that occur prior to the first dose of doxorubicin, during the first cycle of idronoxil + doxorubicin combination treatment, and after the end of the first cycle of combination treatment.

Deaths on study or within 30 days after a patient exits the study will be summarized by treatment. A listing of all deaths will be provided.

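### Section 16.1.1 both includes and excludes worsening of pre-existing conditions as adverse events, so worsening baseline pain or fatigue can go unrecorded in the primary safety tables

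*Combined protocol and SAP*

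**What the plan says.** Section 16.1.1 gives a broad AE definition that takes in "any occurrence that is new in onset or aggravated in severity or frequency from the baseline condition". Its list of things that are not AEs exempts "baseline conditions that have not worsened in severity or frequency", that is, only stable ones. For laboratory findings it adds: "If the laboratory abnormality is a significant change from baseline for the patient, then it should be considered an adverse event".

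The same section later states that "Pre-existing conditions or illnesses which are expected to exacerbate or worsen are not considered adverse events", and assigns them to the medical history.

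Three other places build on the AE definition:

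- Section 14.3.4: "An AE will be deemed treatment emergent (TEAE) if it starts or worsens in severity or toxicity after the beginning of treatment".
- Section 8.1.1: "A DLT will be defined as a protocol-specified adverse event of toxicity Grade 3-4", with related attribution and a pointer to Section 8.3.
- Section 11.1.1 lists AEs first among the primary safety parameters.

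**The concern.** For one class of event, the worsening of a condition that was present at baseline and was expected to worsen, the section gives two opposite instructions.

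That class matters in this trial. Patients have metastatic or recurrent sarcoma, and ECOG status up to 2 is allowed (Section 9.2), so some can be expected to enter with pain or fatigue. Section 8.3.3 names asthenia among the toxicities that NOX66 and doxorubicin may share. Section 6.1 reports Grade 3 asthenia, back pain or bone pain in 3 patients of the NOX66 radiotherapy study.

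Three things are at stake: the completeness of the treatment-emergent (TEAE) tables, consistent recording across about 12 sites, and whether a possible DLT is put forward for assessment.

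**Working it through.** No figure in the plan depends on this point, so the check is mainly a comparison of the texts.

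**1. Where the rules conflict**

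| Baseline condition | AE definition and exclusion list | Closing sentence of 16.1.1 |
|---|---|---|
| Does not worsen | Not an AE | No conflict |
| Worsens, not expected to | AE | Does not apply |
| Worsens, expected to | AE | Not an AE; medical history |

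The conflict is confined to the third row. No section says which rule takes precedence.

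**2. Whether the exclusion is limited.** Two neighbouring rules in Section 16.1.1, on the disease under study and on laboratory changes due to underlying disease, restore AE status when the change exceeds what was expected. The closing sentence has no such limit, and none by grade, cause or relatedness. It therefore applies before the causality assessment in Section 16.1.3 is reached.

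**3. Whether the analysis recovers the event**

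- The TEAE rule in Section 14.3.4 counts worsening, but its starting point is an AE. An event filed as medical history is not one.
- Section 14.3.1 treats missing severity as severe and a missing relationship as definitely related, but only for a reported AE.
- Pain and fatigue are also captured by BPI-SF and EORTC QLQ-FA12. These are secondary quality-of-life measures, summarised on the Full Analysis Set (Section 14.3.11), which requires at least one completed combination cycle (Section 14.2). They do not replace graded AE tables on the Safety Set.

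**4. Laboratory toxicity.** Section 16.1.1 makes a significant laboratory change an AE, and Section 11.4.2.4 does the same for any clinically significant result. Section 14.3.5 tabulates CTC grades and shifts from baseline to worst grade without reference to AE status. Worsening anaemia stays visible.

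**5. The DLT route (Section 8.3.3)**

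- Isolated anaemia is not a DLT. It counts only together with Grade 3 thrombocytopenia, and only if not attributable to doxorubicin.
- Grade 3 fatigue is exempt if it lasts under 1 week. At 1 week or more it qualifies.
- Grade 3 pain is not among the exceptions, so it qualifies if judged related.

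The exposed events are therefore mainly related Grade 3 pain and prolonged Grade 3 fatigue in patients who had the symptom at entry.

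**6. What one missed DLT would do.** Under Section 8.3.2, 1 of 3 read as 0 of 3 means escalation without the three extra patients. A count of 2 of 6 read as 1 of 6 means the level is not declared the DLT level.

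For scale only, let p be the true DLT rate, m the share of DLTs not recorded, and q = p(1 − m). The chance of escalating past a dose level is

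(1 − q)³ + 3q(1 − q)⁵.

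With p = 0.33 and m = 0.20, q = 0.264 and the result is 0.736³ + 3 × 0.264 × 0.736⁵ = 0.399 + 0.171 = 0.570. With m = 0 it is 0.434.

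| p | m = 0 | m = 0.10 | m = 0.20 | m = 0.30 |
|---|---|---|---|---|
| 0.20 | 0.709 | 0.752 | 0.793 | 0.834 |
| 0.33 | 0.434 | 0.500 | 0.570 | 0.641 |
| 0.50 | 0.172 | 0.234 | 0.309 | 0.396 |

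Both p and m are assumptions. The table shows the sensitivity of a 3+3 rule to any missed DLT. It says nothing about how often this sentence would cause one.

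**The case against.** The strongest reply is that the closing sentence concerns the natural course of a co-existing illness, not drug toxicity, and that other text catches what matters. Much of this stands.

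- **Natural course.** This is a plausible reading, and Table 4 schedules medical history only at Screening and Monotherapy Day 1, so a Cycle 1 worsening has no scheduled place there. But the sentence does not say so, and separating illness from drug is the purpose of recording the event and assessing its cause.
- **Events needing treatment.** Section 16.1.1 also makes events that require treatment AEs, which would cover much Grade 3 pain. This is one more rule pointing against the closing sentence, and it does not say which gives way.
- **DLT assessment.** Section 8.3.3 speaks of toxicities judged related and does not require AE-form entry. The Safety Review Committee reviews all data for each cohort (Section 15.2.2.1), including AEs that are not DLTs (Section 15.2.2.3). This is real protection, but it depends on the event being recorded or brought forward.
- **Physical examination.** Section 11.4.2.2 exempts findings described in the past medical history. A reader might take this as a second exclusion of worsening. It is better read as an ambiguously worded rule for new findings, since worsening is itself a change from baseline.

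A reader might also infer that worsening anaemia disappears from the primary safety output and the DLT count, or that serious events are lost. The documents do not support either. Anaemia is covered in steps 4 and 5. Section 16.1.2 defines serious events by untoward occurrence and outcome, and Section 16.2 requires their reporting whether or not related. Neither relies on the closing sentence.

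**Conclusion.** The text is wrong as written: Section 16.1.1 contradicts itself on expected worsening of a pre-existing condition and gives no precedence. The consequence is possible under-recording, and uneven recording between sites, of worsening non-laboratory symptoms present at baseline, mainly pain and fatigue, in the TEAE tables. A secondary and partly protected risk is that related Grade 3 pain, or Grade 3 fatigue of 1 week or more, is not put forward for DLT assessment.

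The size cannot be estimated. The documents do not give the share of patients entering with these symptoms, how many would worsen, or how many sites would follow the closing sentence. The conclusion rests only on some sites applying that sentence as written. This should be fixed because it governs capture of a primary safety parameter, but the limits above do not support treating it as a critical defect.

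**What to change.** In Section 16.1.1, delete the closing sentence on pre-existing conditions, or limit it to those that have not worsened. Add that any pre-existing condition that worsens in CTCAE grade, severity or frequency after the first dose is recorded as an AE at its new grade, whether or not the worsening was expected. Keep the separate handling of sarcoma progression.

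In Section 11.4.2.2, keep the rule but clarify that worsening of a condition in the medical history counts as a change to be recorded.

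The cost is two edited passages, site training, somewhat more AE entries and slightly higher reported AE rates. No dose, treatment or escalation rule changes.

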16.1.2 SERIOUS ADVERSE EVENTS

The definitions of SAEs are given below. The Investigator is responsible for ensuring that all staff involved in the trial are familiar with the content of this section.

A SAE or reaction is defined as any untoward medical occurrence that results in any of the following outcomes:

- Death
- Life-threatening adverse drug experience defined as any adverse drug experience that, in the opinion of the Investigator, places the patient at immediate risk of death from the reaction as it occurred. It does not include a reaction that, had it occurred in a more severe form, might have caused death.
- An in-patient hospitalization or prolongation of existing hospitalization
- Persistent or significant disability/incapacity, defined as “A substantial disruption of a person’s ability to conduct normal life functions”
- Congenital anomaly/birth defect (in the offspring of a patient)

The definition of SAE also includes any important medical event. Medical and scientific judgment should be exercised in deciding whether expedited reporting is appropriate in other situations, such as important medical events that may not be immediately life-threatening or result in death or hospitalization, but may jeopardize the patient or may require intervention to prevent one of the other outcomes listed in the previous definition. These should also usually be considered serious. Examples of such events are intensive treatment in an emergency room or at home for allergic bronchospasm; blood dyscrasias or convulsions that do not result in hospitalization; or development of drug dependency or drug abuse. Progression of malignancy (including fatal outcomes), if documented by the use of an appropriate method (for example, as per RECIST v1.1 criteria for solid tumors), should not be reported as an SAE and must be approved by the Sponsor.

Treatment within or admission to the following facilities does not meet the criteria of ‘in-patient hospitalization’ (although if any other SAE criteria are met, the event must still be treated as an SAE and immediately reported):

- Emergency Department or Emergency Room
- Outpatient or same-day surgery units

- Observation or short-stay unit
- Rehabilitation facility
- Hospice or skilled nursing facility
- Nursing homes, custodial care or respite care facility

Hospitalization during the trial for a pre-planned surgical or medical procedure (one which was planned prior to entry in the trial), does not require reporting as a SAE to the Medical Monitor and Sponsor.

The definition of 'related' is that there is a reasonable possibility that the drug caused any of the adverse events described in [Table 5](#).

16.1.3 GUIDELINES FOR DETERMINING CAUSALITY AND SEVERITY

The Investigator must assign a relationship of each adverse event to the receipt of the investigational product (NOX66 or the combination of NOX66 and doxorubicin). The Investigator will use clinical judgment to assess a plausible biologic mechanism for a temporal relationship between the onset of the event in relation to receipt of the investigational product, and the Investigator may determine possible alternate etiologies including underlying disease, concurrent illness or concomitant medications. The following guidelines should be used by Investigators to assess the relationship of an adverse event to study product administration.

The criteria used for determining the relationship between the study drug/s and the Adverse Event are shown below.

Table 5 Relationship to Study Drug

Unlikely/unrelated	An AE with a temporal relationship to drug administration, which makes a causal relationship improbable, and in which other drugs, chemicals or underlying disease provide plausible explanations.
Possible	An AE with a reasonable time sequence to administration of the drug, but which could also be explained by concurrent disease or other drugs or chemicals. Information on drug withdrawal may be lacking or unclear.
Likely	An AE with a reasonable time sequence to administration of the drug, unlikely to be attributed to concurrent disease or other drugs or chemicals, and which follows a clinically reasonable response on withdrawal (rechallenge) . Rechallenge information is not required to fulfil this definition.
Certain	An AE occurring in a plausible time relationship to drug administration and cannot be explained by concurrent disease or other drugs or chemicals. The response to withdrawal of the drugs should be clinically plausible. The event must be definitive pharmacologically or phenomenologically using a satisfactory rechallenge procedure if necessary and feasible.

Hospitalization for elective surgery related to a pre-existing condition, routine clinical procedures, or social reasons that did not increase in severity or frequency after beginning the study are not considered to be AEs but must be recorded in the source documents. If the hospitalization is due to a pre-existing condition or was planned prior to the start of the study, the condition that led to the hospitalization should be recorded in the eCRF Medical History form. If the hospitalization arises from a pre-existing condition that did not worsen and the hospitalization was planned after the start of the study, the condition that led to hospitalization should be recorded in the AE page of the eCRF. In both cases, the condition that led to hospitalization should be recorded, and the relationship to study drug will be recorded as "Unrelated."

16.1.4 ACTION TAKEN AND OUTCOME

The Action Taken with NOX66 and doxorubicin for every AE will be reported as either "Dose Not Changed", "Dose Reduced", "Dose Withdrawn" or "Dose Delayed". The Outcome of each AE will be entered as either: Resolved, Resolved with Sequelae, Ongoing, Death, or Unknown as noted in [Table 6](#).

Table 6 Adverse Event Outcome Category

'Resolved'	The patient has fully recovered from the adverse event with no residual effects observable.
'Resolved with Sequelae'	The patient has recovered from the adverse event, however there are residual effects observable.
'Ongoing'	The adverse event is still present and observable.
'Death'	The patient died as a result of the adverse event.
'Unknown'	The outcome of the adverse is unknown at the time of report.

16.2 RESPONSIBILITIES FOR REPORTING

Investigators and the Sponsor are required by regulatory agencies worldwide to report adverse events which involve patients being administered a pharmaceutical product.

All serious adverse events (SAE) occurring from the signing of informed consent until 30 calendar days after last study treatment, whether related to drug or not, must be reported to the Medical Monitor and appropriate Sponsor contact person within 24 hours of first knowledge of the experience using the appropriate study SAE Report Form. SAEs are to be followed until resolution or stabilization (with autopsy report if applicable).

Deaths and other SAEs occurring > 30 calendar days after last study treatment that are deemed 'possibly' or 'probably' related to the study treatment must be reported as SAEs on the SAE Report Form within 1 day of first knowledge of the event by the treating physician or research personnel (with an autopsy report if available).

Deaths occurring > 30 calendar days after study trial treatment and not attributed to study treatment (e.g., disease progression) need not be reported as SAEs, but simply captured on the appropriate CRF.

16.2.1 SAE AND UNRESOLVED AE FOLLOW-UP

Follow-up information for SAEs and information on non-serious AEs that become serious should also be reported to the Medical Monitor as soon as possible using the SAE Report Form. The patient should be followed until it is determined that the event resolved, stabilized, or in the opinion of the Investigator the event is not going to improve due to underlying disease, or the patient dies or is lost to follow-up.

Investigators must report SAEs and follow-up information to their responsible IRB according to the policies of the responsible IRB.

The detailed SAE reporting process will be provided to the sites.

